## Protocol P3P-PK-01-CH

## Statistical Analysis Plan

Final v2.0 / 30 Apr 2018

Confidential

Page 38 of 90

we are expecting a low drop-out rate, 3 subjects will be allocated to each sequence. Therefore, 18 subjects will be randomized.

A sufficient number of eligible subjects will be enrolled and exposed to P3P 3 at Admission (Day -1) and Day 1 to ensure randomization of 18 subjects to one of six possible sequences at Day 2.

A sensitivity analysis was added in Section 12.6.1 "Primary Analyses" to evaluate the impact of including the Study Day in the analysis of specific PK parameters.

The definitions of enrolled population and randomized population were added

No shift table for ECG data will be provided.

## 10 ANALYSIS POPULATIONS

All endpoints (other than safety) will be analyzed using the PK population. Safety will be analyzed using the safety population.

## 10.1 Screened Population

The screened population consists of all the subjects who signed ICF.

## 10.2 Enrolled Population

The enrolled population is a subset of the screened population consisting of all the subjects with enrollment or randomization date, or have at least one exposure to P3P (including the product test at Admission).

### 10.3 Randomized Population

The randomized population is a subset of the enrolled population consisting of all the subjects with a randomization date.

## 10.4 PK Population

The PK population consists of all the subjects in Screened Population who completed at least one single use of P3P (during Day 1 to Day 4) and for whom at least one primary nicotine PK parameter can be derived. Subject with major protocol deviations that impact evaluability of the data will be excluded the PK populations (see Section 11.1 "Major Protocol Deviations").

## 10.5 Safety Population

The safety population consists of all subjects in Screened Population who have at least one exposure to P3P (including the product test at Admission) and have at least one safety assessment post exposure.

## 11 PROTOCOL DEVIATIONS

Protocol deviations are defined as those deviations from any procedure as defined in the Study Protocol, including but not limited to, any violation of inclusion/exclusion criteria, mis-randomizations, use of any nicotine or tobacco-containing product other than the assigned product during each of the exposure period, use of any nicotine tobacco-containing product during washout periods, assessments not performed or performed outside the scheduled time windows, or use of oestrogen or other drugs that are known to affect CYP2A6 activity.

Information following site monitoring and other reviews will be documented in the site visit reports, follow-up letters, audit documentation, or other manual review and subsequently recorded in the CRO Deviation Tracking System (CDTS). Additional protocol deviations may be identified in the data review, these will also be recorded in the CDTS. All protocol deviations will be imported into the DV domain of the Study Data Tabulation Model (SDTM).datasets/Analysis Data Model (ADaM).

All deviations will be reviewed to determine their impact when subjects are assigned to analysis populations. Each deviation will be classified as major or minor; all major deviations will be further reviewed to determine whether or not the deviation impacts the evaluability of the results and therefore should result in the subject being excluded from the PK population.

### 11.1 Major Protocol Deviations

The following categories for the major deviations will include, but are not limited to the deviations presented in Table 14.

**Table 14 Definition of Major Protocol Deviations**

Category	Description
Entry Violation	Violation of inclusion/exclusion criteria
Mis-randomization	Violation of the product allocation process, including but not limited to the misclassification of subject's sex at randomization and incorrect P3P variant administered according to randomized sequence
Mis-use of product	

Use of any nicotine or tobacco-containing product other than P3P 3 at Day 1 or allocated P3P variants from Day 2 to Day 4 during the exposure periods, or use of any nicotine tobacco-containing product during wash-out hours.

#### Confidentiality Statement

**Table 14 Definition of Major Protocol Deviations**

Category	Description
	

Product use not compliant with planned regimen (e.g., number of puffs during the fixed regimen)

Concomitant medication	Use of any drugs which are known to affect CYP2A6 activity

Among the above criteria, violations of inclusion criteria 1, 2, 4, 5 and 7, or of the exclusion criteria 2 and 15 will be considered as impacting the evaluability. Other major protocol deviations will be assessed for their impact on the PK Population and evaluated during the pre-analysis data review meeting (Section 6.3.2 "Methods of Assigning Subjects to Treatment Sequences").

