2.3.3 Anticipated Foreseeable Risks due to Investigational Product

Although by product design, P3P does not generate toxins and carcinogens as observed with cigarette smoking (10), given the current state of knowledge of the product, it has not been demonstrated that P3P reduces the risk of developing smoking-related diseases compared to cigarettes.

Due to sensorial and technological differences between P3P and cigarettes, it is possible that subjects will adapt their behavior, e.g., by modifying the number, the volume and/or duration of puffs, as well as the intensity of inhalation. A confinement setting may also have an influence on puffing behavior and may lead to an increase of P3P use when *ad libitum* use is allowed.

An adult smoker using P3P may experience:

- Transient nicotine withdrawal symptoms (e.g., urge to smoke, irritability, anxiety feelings, restlessness, and difficulty to concentrate) similar to cravings observed during smoking cessation
- Transient symptoms suggesting mild nicotine overdose such as stimulatory effects on sympathetic tone (increased blood pressure, increased heart rate), central nervous system (tremor, blunting of emotions, and decreased ability to concentrate), gastric acid secretion, and vomiting. Individuals who experience AEs (suggesting excessive stimulant effects) should be instructed to reduce their intensity of product use by decreasing the number of puffs and/or the intensity of puffing
- Change in smoking habits due to study requirements and related concomitant symptoms, e.g., craving

Support during periods of smoking abstinence will be provided. Further risk mitigation will include:

- Using commonly accepted research and scientific standards (e.g., blood samples not to exceed blood donation standards)
- Medical supervision of all study subjects with follow-up of those who have experienced an AE(s)/SAE(s)

Confidentiality Statement

Data and information contained in this document are considered to constitute trade secrets and confidential commercial information, and the legal protections provided to such trade secrets and confidential information are hereby claimed under the provisions of applicable law. No part of this document may be publicly disclosed without the written consent of Philip Morris Products S.A.

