6.2 Use of Investigational Products

Subjects will never be forced to use P3P and will be free to stop using P3P at any time during the study.

Confidentiality Statement

Data and information contained in this document are considered to constitute trade secrets and confidential commercial information, and the legal protections provided to such trade secrets and confidential information are hereby claimed under the provisions of applicable law. No part of this document may be publicly disclosed without the written consent of Philip Morris Products S.A.

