6.2.2 Investigational Period (Day 1 to Day 5)

Each subject will use P3P 3 on Day 1. In the morning of Day 2, subjects will be randomized to one of six sequences in order to cross-over to the use of P3P 1, P3P 2 and P3P 4 on Days 2, 3 and 4 (section 6.3).

On each assessment day (Day 1 to Day 4), following at least 10 hours of abstinence from any tobacco and nicotine containing products, subjects will use the assigned product for the given visit with two product use regimen as described in Figure 2:

- using a fixed puffing regimen comprising of 12 puffs in total at a rate of one inhalation every 30 seconds (\pm 5 seconds) in the morning.
- using *ad libitum* use period for 60 minutes (\pm 5 minutes) in the afternoon.

A puffing topography device will be attached to each P3P. There will be one recording of HPT parameters per product. Each P3P product will be weighed before and after product use to estimate the amount of nicotine delivered in the aerosol. During the *ad libitum* use period, the subjects can use the product according to their puffing behavior, without restrictions in the number of puffs, interpuff interval duration or number of products used. The number of P3P products used during the *ad libitum* use period will be recorded. The start and stop time of each product used during each puffing regimen will be recorded as well as the total number of puffs taken at the fixed puffing regimen.

The start of product use for fixed puffing and for the *ad libitum* use period will be defined as T_0 fix and T_0 ad lib, respectively. There will be a washout period of 10 hours between T_0 fix and T_0 ad lib.

There will be no product use on the Discharge day (Day 5).

Except for the assigned products, subjects will not be allowed to use any nicotine-containing products through Discharge or early termination.

Subjects will be continuously supervised by the investigational site staff during P3P use.

Confidentiality Statement

Data and information contained in this document are considered to constitute trade secrets and confidential commercial information, and the legal protections provided to such trade secrets and confidential information are hereby claimed under the provisions of applicable law. No part of this document may be publicly disclosed without the written consent of Philip Morris Products S.A.

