6.2.4 Stopping Rules for Investigational Product

For safety purposes, use of P3P should be temporarily reduced (decreasing number or/and intensity of puffs) or stopped in the event of any signs suggesting nicotine overexposure, e.g., gastrointestinal disturbance (nausea, vomiting, diarrhea, stomach or abdominal pain), cold sweats, headache, dizziness and breathing problems, or any reasons at the discretion of the Investigator.

In the morning of Day 2 subjects will be randomized after confirmation that there are no safety concerns based on the Investigator's judgement.

For subjects who are discontinued, the reason for discontinuation should be documented in the source documents and in the CRF and subjects will undertake early termination procedures (section 9.6).

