12.3.1 Pharmacokinetic Population

The nicotine exposure analysis sets consist of all the enrolled subjects who gave informed consent, completed at least one of the single use of P3P, and for whom at least one primary nicotine PK parameter can be derived. Only subjects without major protocol deviations will be included in the nicotine exposure analysis sets.

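### The SAP classes an off-plan puff count in the fixed regimen as major mis-use, although the protocol directs fewer puffs or stopping on signs of nicotine overexposure; the whole subject can then leave every non-safety analysis

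*SAP*

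**What the plan says.** The fixed regimen is defined in protocol 6.2.2 as "comprising of 12 puffs in total at a rate of one inhalation every 30 seconds". Three protocol passages foresee that a subject may take fewer:

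- Section 6.2.4: "use of P3P should be temporarily reduced (decreasing number or/and intensity of puffs) or stopped in the event of any signs suggesting nicotine overexposure".
- Section 2.3.3: subjects with adverse events that suggest excessive stimulation "should be instructed to reduce their intensity of product use by decreasing the number of puffs and/or the intensity of puffing".
- Section 6.2: subjects "will be free to stop using P3P at any time during the study".

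SAP Table 14 then gives as an example of a major deviation, in its mis-use row: "Product use not compliant with planned regimen (e.g., number of puffs during the fixed regimen". It makes no exception for a reduction made under 6.2.4.

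The consequence is stated in three places, not in the same way. Protocol 12.3.1: "Only subjects without major protocol deviations will be included in the nicotine exposure analysis sets". SAP 10.4: "Subject with major protocol deviations that impact evaluability of the data will be excluded the PK populations". The protocol synopsis agrees with the SAP in tying exclusion to evaluability. SAP 11.1 names certain entry-criterion violations that always affect evaluability; puff count is not among them. For the rest: "Other major protocol deviations will be assessed for their impact on the PK Population and evaluated during the pre-analysis data review meeting".

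SAP section 10 uses the PK population for every endpoint other than safety.

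**The concern.** Protocol 11.1.2 defines a deviation as a departure from protocol procedures, and protocol 8.7 defines misuse as use that does not follow the product's instruction. A reduction that the protocol itself directs fits neither definition, yet it falls under the words of Table 14.

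The penalty applies to the subject and not to the session, which is costly in a crossover. A subject who stops early on one morning could lose all four variants, both regimens, VAS craving, mCEQ, sensory questionnaire, topography and product weights. The trigger is a sign of nicotine effect, so removal may be related to exposure. Absolute levels matter here: the primary objective is the profile of each variant, and protocol 4.2 wants to learn which nicotine content comes closest to the concentrations after a single cigarette. The mCEQ aversion items (dizziness, nausea) would also lose subjects likely to report them.

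Timing adds to this. The study is open label. The sponsor reviews an interim report with unadjusted PK by variant before database lock (SAP 13.1.4), and the data review meeting that decides exclusions is also before lock (SAP 13.5). The section number that SAP 11.1 cites for that meeting, 6.3.2, is the section on blinding and holds no evaluability rule.

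**Working it through.** **1. The plan's own figure.** Three variants give 3! = 6 orders; 6 × 3 subjects = 18, as stated. No alpha, power, effect size or SD is given, so what follows is illustration.

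**2. Data lost for one short session.** Each subject has 4 days × 2 regimens = 8 sessions, so the trial has 18 × 8 = 144. Loss of the session costs 1/144 = 0.7%; loss of the subject costs 8/144 = 5.6%.

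**3. How often it might arise.** For an assumed per-subject probability p of at least one directed reduction, P(at least 1 of 18) = 1 − (1 − p)^18, and P(at least 2) subtracts a further 18p(1 − p)^17.

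| Assumed p | At least 1 | At least 2 |
|---|---|---|
| 5% | 60% | 23% |
| 10% | 85% | 55% |
| 20% | 98% | 90% |

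**4. Precision.** With 4n observations, n subjects, 3 variant and 2 day terms, the residual df are 3n − 5. The CI half-width for a contrast is proportional to t(0.975; 3n − 5)/√n. For n = 18 this is 2.0096/√18 = 0.4737; for n = 17 it is 2.0129/√17 = 0.4882. The ratio is 1.031. Removal of 1, 2, 3 or 4 subjects widens the interval by about 3%, 6%, 10% or 14%.

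**5. Per-variant level, worst case.** Suppose that the subjects removed are exactly the highest exposed. The expected top three of 18 standard normal values are 1.820, 1.350 and 1.066. After removal of the top one the mean of the rest is −1.820/17 = −0.107; of the top two, −3.170/16 = −0.198; of the top three, −4.236/15 = −0.282. Multiply by σ = √ln(1 + CV²) and exponentiate. At CV 50%, σ = 0.472, and exp(−0.472 × 0.107) = 0.951, a fall of 4.9%.

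| Removed | CV 30% (σ 0.294) | CV 50% (σ 0.472) | CV 70% (σ 0.631) |
|---|---|---|---|
| 1 | 3.1% | 4.9% | 6.5% |
| 2 | 5.7% | 8.9% | 11.8% |
| 3 | 8.0% | 12.5% | 16.3% |

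A simulation (40,000 trials) that adds within-subject CVs of 20% to 40%, and removes the subjects with the highest single-session value, gives 3–7%, 6–12% and 8–17%.

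**6. Variant ratios.** In the same simulation, a true P3P 2 / P3P 3 ratio of 2.00 moves to between 1.92 and 2.00 when 1 to 4 subjects are removed. The contrast is within subject, so a subject's general level cancels.

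**The case against.** A reader might infer that the plan will remove the most exposed subjects and so distort the comparison of variants. The documents do not support that.

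- **Removal is not automatic under the SAP.** SAP 11 requires a second review of every major deviation, and the synopsis agrees. This stands. But protocol 12.3.1 says otherwise, and neither document tells the review what would make a short session non-evaluable.
- **There is some exclusion below subject level.** SAP 7.1.3 permits documented exclusion of anomalous concentrations and gives interrupted use in the fixed regimen as an example. This stands, so it would be wrong to say that nothing exists between full retention and full removal. It covers concentrations that do not fit the expected profile, however. A session of eight puffs with a smooth, lower curve need not be anomalous.
- **A directed reduction can be read as no deviation at all.** That is the sensible reading of protocol 11.1.2 and 8.7, but Table 14 gives puff number as its own example and does not say it.
- **Most exposed is an inference.** Dizziness or nausea is not a concentration. A subject with low tolerance may stop early with a low Cmax. A reduction in intensity alone would not change the puff count either. The figures in step 5 are a worst case.
- **Safety reporting and transparency.** Adverse events stay in the safety population with the action taken; puff counts (SAP 12.5) and reasons for exclusion (SAP 12.2) are reported. This stands. Transparency limits the harm but does not replace a rule.

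**Conclusion.** The conflict is in the text and should be repaired. Behaviour that the protocol directs is classed as major mis-use, and its consequence falls on the whole subject: automatic under protocol 12.3.1, discretionary and without a criterion under SAP 10.4 and 11.1.

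The size is modest. One removal costs 5.6% of the sessions instead of 0.7% and widens the contrast intervals by about 3%. A bias of about 3% to 7% in the geometric mean for one removal, or 6% to 12% for two, holds only if those removed are the most exposed and the between-subject CV is 30% to 70%; both are assumptions. N = 18 is also one, because SAP 10.4 could admit subjects with Day 1 data who were not randomized. The three planned ratios are little affected, no hypothesis is tested, and the conflict is confined to the fixed regimen, since ad libitum use has no set puff number.

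**What to change.** Leave the clinical rule as it is, and reconcile protocol 6.2.4, protocol 12.3.1 and SAP 10.4 and 11.1.

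1. In Table 14, state that a reduction or stop made under protocol 6.2.4 is not mis-use and is not by itself a ground to remove the subject.
2. Decide the evaluability of a short fixed-puffing session at session level, by a written rule fixed before PK results are seen. Keep the subject's other sessions, ad libitum data and questionnaires. The SAP revision history shows that draft interim PK results had been reviewed before version 2.0. A rule added after that should say so and rest on puff count and reason only.
3. Flag short sessions from data already collected: the recorded puff count, and the adverse-event action taken (reduced, interrupted, stopped).
4. Report the fixed-regimen PK summary and model with and without the flagged sessions. Do not drop them from the primary model by default: that would itself be informative, and unevenly so across variants.
5. Correct the cross-reference in SAP 11.1.

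The cost is a few sentences, one flag and one extra display. The data become slightly unbalanced, which the planned mixed model can handle.

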## 11.2 Minor Protocol Deviations

The categories for the minor deviations will include, but are not limited to the deviations presented in Table 15.

**Table 15 Definition of Minor Protocol Deviation Categories**

Category	Description
Procedural violation	Violation of any study procedures not affecting safety or data evaluability
Time deviation (Plasma nicotine PK sample)	Assessments not taken at the correct time or within the allowed time window or date/time is missing (see Table 16)
Time deviation (other assessment)	Assessments not taken at the correct time or within the allowed time window or date/time is missing (see Table 16)
Assessment missing (Plasma nicotine PK sample)	Assessment is missing
Assessment missing (other assessment)	Assessment is missing
Randomization sequence	Subject randomized not according to the sequence of the subject numbers assigned during the screening visit

## 11.3 Assessment Windows

Definition of Assessment Windows is described in Table 16:

**Table 16 Definition of Assessment Windows**

Assessment	Nominal Time point(s) (relative to <math>T_0</math> fix or <math>T_0</math> ad lib)	Window
Plasma nicotine PK sample	15 minutes prior to $T_0$ fix	$\pm$ 5 minutes
	2 minutes after $T_0$ fix	$\pm$ 1 minute
	4 minutes after $T_0$ fix	$\pm$ 1 minute
	7 minutes after $T_0$ fix	$\pm$ 1 minute
	10 minutes after $T_0$ fix	$\pm$ 1 minute
	15 minutes after $T_0$ fix	$\pm$ 2 minutes
	30 minutes after $T_0$ fix	$\pm$ 2 minutes
	1 hour after $T_0$ fix	$\pm$ 5 minutes
	2 hours after $T_0$ fix	$\pm$ 5 minutes
	4 hours after $T_0$ fix	$\pm$ 5 minutes
	15 minutes prior to $T_0$ ad lib	$\pm$ 5 minutes
	10 minutes after $T_0$ ad lib	$\pm$ 1 minute
	20 minutes after $T_0$ ad lib	$\pm$ 2 minutes
	30 minutes after $T_0$ ad lib	$\pm$ 2 minutes
	40 minutes after $T_0$ ad lib	$\pm$ 5 minutes
	1 hour after $T_0$ ad lib	$\pm$ 5 minutes
	2 hours after $T_0$ ad lib	$\pm$ 5 minutes
	4 hours after $T_0$ ad lib	$\pm$ 5 minutes
	14 hours after $T_0$ ad lib (*)	$\pm$ 30 minutes
	16 hours after $T_0$ ad lib (*)	$\pm$ 30 minutes
	18 hours after $T_0$ ad lib (*)	$\pm$ 30 minutes
	20 hours after $T_0$ ad lib (*)	$\pm$ 30 minutes
	24 hours after $T_0$ ad lib (*)	$\pm$ 30 minutes
Visual Analog Scale Craving	- 15 minutes prior to $T_0$ fix	$\pm$ 5 minutes
	4 minutes after $T_0$ fix	$\pm$ 2 minutes
	10 minutes after $T_0$ fix	$\pm$ 2 minutes
	15 minutes after $T_0$ fix	$\pm$ 2 minutes
	30 minutes after $T_0$ fix	$\pm$ 5 minutes
	1 hour after $T_0$ fix	$\pm$ 10 minutes
	2 hours after $T_0$ fix	$\pm$ 10 minutes
	4 hours after $T_0$ fix	$\pm$ 10 minutes

**Table 16 Definition of Assessment Windows**

Assessment	Nominal Time point(s) (relative to $T_0$ fix or $T_0$ ad lib)	Window
	15 minutes prior to $T_0$ ad lib	$\pm$ 5 minutes
	10 minutes after $T_0$ ad lib	$\pm$ 2 minutes
	20 minutes after $T_0$ ad lib	$\pm$ 2 minutes
	30 minutes after $T_0$ ad lib	$\pm$ 5 minutes
	40 minutes after $T_0$ ad lib	$\pm$ 5 minutes
	1 hour after $T_0$ ad lib	$\pm$ 10 minutes
	2 hours after $T_0$ ad lib	$\pm$ 10 minutes
	4 hours after $T_0$ ad lib	$\pm$ 10 minutes
Adapted mCEQ	On Day 1, 2, 3 and 4	Within 60 minutes after the end of ad libitum product use
Sensory Questionnaire	On Day 1, 2, 3 and 4	Within 60 minutes after the end of ad libitum product use
Cough Assessment	On Day -1 prior to product test 24 hours after $T_0$ fix for each variant (performed on Day 2, 3, 4 and 5)	$\pm$ 1 hour
Vital Signs	Screening Day -1 Pre fixed puffing on Day 1, 2, 3 and 4 60 minutes post fixed puffing on Day 1, 2, 3 and 4 60 minutes after the end of ad libitum product use on Day 1, 2, 3 and 4 Day 5 Early Termination	Not applicable Not applicable Within 1 hour prior to product use $\pm$ 10 minutes $\pm$ 10 minutes Not applicable Not applicable

(\*) Applicable only at Day 5

